3.9. Efficacy Estimands

Three efficacy estimands: a treatment-policy estimand, a hypothetical estimand and a composite estimand, are defined for the primary and secondary efficacy endpoints.

The **treatment-policy estimand** is the primary estimand for the primary and secondary efficacy endpoints.

1) Population: Subjects in the FAS

- 2) Variable: Primary and secondary endpoints
- 3) Intercurrent events: The occurrence of an intercurrent event is irrelevant. All observed values will be used regardless of occurrence of an intercurrent event

The **hypothetical estimand** is defined as following. This is the supportive estimand for the primary and secondary efficacy endpoints.

- 1) Population: Subjects in the Full Analysis Set (FAS).
- 2) Variable: Primary and secondary endpoints
- 3) Intercurrent events: The following intercurrent events are taken into account:
 - Subject takes prohibited medication
 - Subject changes the dose of the medication required to be stable per protocol
 - Subject discontinues from study treatment

The **composite estimand** is defined as following. This is the supportive estimand for the primary and secondary efficacy endpoints.

- 1) Population: Subjects in the Full Analysis Set (FAS).
- 2) Variable: Primary and secondary endpoints
- 3) Intercurrent events: The following intercurrent events are taken into account:
 - Subject takes prohibited medication
 - Subject changes the dose of the medication required to be stable per protocol
 - Subject discontinues from study treatment

The estimators associated with each of these estimands are described in [Table 3](#) of Section 6.

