1.7. Risk/Benefit Assessment for the Study

Sjogren's Syndrome is a chronic, systemic inflammatory disease that affects approximately 1% of the population. Currently, there are no DMARDs approved for the treatment of SjS. The need for new, therapeutic options with a favorable efficacy and safety profile has prompted efforts to evaluate orally administered, small molecules in this disease setting.

Please refer to respective Investigator's Brochures (IB) for updated safety information and risk/benefit assessment.

Filgotinib, a once-daily, oral, and potent JAK-1 inhibitor, is being developed for the treatment of RA and other autoimmune diseases. In the ongoing and concluded studies, filgotinib has been generally safe and well tolerated. The primary endpoint was achieved in two large dose ranging studies (GLPG-CL-203 and GLPG-CL-204) evaluating the effect of filgotinib on RA disease activity. However, a potential increased risk of infection may be considered consistent with the mechanism of JAK inhibition. In the filgotinib RA program, deaths were reported due to infectious etiologies.

Nonclinical studies in rats and dogs identified lymphoid tissues and testes as target organs for filgotinib; microscopic findings in the testes included germ cell depletion and degeneration in both species, with reduced sperm content and reduced fertility in male rats. The clinical relevance of nonclinical testicular findings in rats and dogs is unknown. A male safety study is ongoing to assess the effects, if any, of filgotinib on semen parameters in males with inflammatory diseases. Until the definite results of this study are available, all males will be informed about this potential toxicity in the informed consent form and only men understanding and accepting the potential risk for loss of fertility will be enrolled. In addition SjS is a disease of female predominance and depending on the study population the incidence of SjS in females is reported to be 10 to 20 fold higher in females than males {Patel 2014}.

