6. EFFICACY ANALYSES

Efficacy endpoints will be evaluated for the following treatment periods: placebo-controlled period up to Week 24 and the entire study up to Week 48.

The primary and secondary endpoints analyses will be based on the estimands presented in the [Table 3](#).

Table 3. Efficacy Estimands

Binary Endpoint	Treatment Policy (main)	Hypothetical	Composite
Population	FAS	FAS	FAS
Intercurrent Event	Ignore all intercurrent events	
 • Treatment discontinuation • Start of prohibited medication • The dose change of medication that is required to be stable Data after the event are treated as missing	
 • Treatment discontinuation • Start of prohibited medication • The dose change of medication that is required to be stable Data after the event are treated as no response
Main Estimator	Stratified CMH test with imputation of missing data using logistic regression	Stratified CMH test with imputation of missing data using logistic regression	Stratified CMH test with non-responder imputation of missing data

Continuous Endpoints	Treatment Policy (main)	Hypothetical	Composite
Intercurrent Event	Ignore all intercurrent events	
 • Treatment discontinuation • Start of prohibited medication • The dose change of medication that is required to be stable 	
 • Treatment discontinuation • Start of prohibited medication • The dose change of medication that is required to be stable
Main Estimator	The treatment difference will be estimated using a mixed effects model for repeated measures. Missing data will be imputed using multiple imputation	The treatment difference will be estimated using a mixed effects model for repeated measures. Missing data will be imputed using multiple imputation	The treatment difference will be estimated using a mixed effects model for repeated measures. Missing data will be imputed using multiple imputation based on observed data from the placebo group

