6.1. Multiple Imputations of Missing Data

Multiple imputation of binary variables: The MI procedure replaces each missing binary response value with a set of plausible values that represent the uncertainty about the right value to impute. Twenty imputed datasets will be generated based on logistic regression models. These multiple imputed data sets are then analyzed by using the same method for the primary analysis for complete data as specified in Section 6.3. The results from each set of imputed data sets will then be combined using Rubin's rule {Rubin 1987}. Stratification factors will be included in the imputation model.

Multiple imputation of continuous variables: All subjects with baseline measurement will be included. The MI procedure replaces each missing value with a set of plausible values that represent the uncertainty about the right value to impute. Twenty imputed datasets will be generated based on linear regression models on observed values. These multiple imputed data sets are then analyzed by using the analysis method specified in Section 6.4 for complete data. The result of each imputed data set will be combined using Rubin's rule {Rubin 1987}. Stratification factors and baseline values will be included in the imputation model as covariates.

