6.3. Analysis for the Primary Efficacy Endpoint

6.3.1. Primary Analysis of Primary Endpoint

In the primary analysis, the primary outcome in each active treatment group will be compared to the outcome in the placebo group using a superiority test at the 2-sided 0.05-level. The following null hypotheses will be tested (vs. the respective alternative hypotheses):

- H01: There is no difference in the responder rate between filgotinib 200 mg group and placebo group at Week 12
- H02: There is no difference in the responder rate between lanraplenib 30 mg group and placebo group at Week 12
- H03: There is no difference in the responder rate between tirabrutinib 40 mg group and placebo group at Week 12

The analyses will be performed using Cochran Mantel Haenszel (CMH) test adjusted for the randomization stratification factors. If CMH test stratified by both stratification factors is not appropriate due to small cell counts then the levels of the stratification by ESSDAI scores will be pooled, and the analysis will be stratified only by use of concurrent immunomodulatory drugs at baseline. Each of the three hypotheses will be tested separately at the 2-sided, 0.05-level.

The primary analysis will be based on the Treatment Policy Estimand, with missing values imputed by multiple imputation method described in Section 6.1.

The number and percentage of responders in each treatment group as well as 95% confidence intervals (CIs) will be presented for each visit.

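### The main estimand makes no exception for death, so a subject who dies before Week 12 with no Week 12 value would have a response imputed in the primary analysis

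*SAP*

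**What the plan says.** SAP 3.9 names three estimands and makes treatment policy the primary one. Its rule for intercurrent events is "The occurrence of an intercurrent event is irrelevant. All observed values will be used regardless of occurrence of an intercurrent event". In SAP Section 6, Table 3 repeats this for the binary endpoint as "Ignore all intercurrent events" and gives the estimator as "Stratified CMH test with imputation of missing data using logistic regression".

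SAP 6.3.1 carries this into the primary test: "The primary analysis will be based on the Treatment Policy Estimand, with missing values imputed by multiple imputation method described in Section 6.1". SAP 6.1 describes the step: "The MI procedure replaces each missing binary response value with a set of plausible values", and "Twenty imputed datasets will be generated based on logistic regression models". The only terms it names for the binary imputation model are the stratification factors.

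Three other places complete the picture:

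- SAP 3.1.2 keeps every randomized and dosed subject in the Full Analysis Set (FAS).
- SAP Appendix 2 sets the primary endpoint to missing when a post-baseline visual analogue scale (VAS) value is missing.
- Death appears in the rule for imputing the last dose date (SAP 4.2.1) and in the safety summaries and listings (SAP 7.1.6). It appears in no efficacy rule.

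**The concern.** A treatment-policy strategy uses the outcome seen after the intercurrent event, whatever the event was. That works for stopping study drug or taking a prohibited medicine. It cannot work for death, because no later outcome exists. With no exception written, the subject passes from the estimand rule to the missing-data rule, and the primary analysis fills in the response the subject might have had if alive. For that subject the estimand and the estimator no longer match.

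At stake is the headline comparison, in which an arm would be credited with a fraction of a responder for a subject who died. The SAP names nothing in the imputation model that would pull such a draw towards non-response. Protocol 1.7 shows that the event is conceivable: "In the filgotinib RA program, deaths were reported due to infectious etiologies".

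**Working it through.** **Path of one subject through the rules.** Take a subject who is dosed, dies at Week 6 and has no value assigned to Week 12.

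1. Dosed, so in the FAS (SAP 3.1.2).
2. No Week 12 VAS, so the response is missing (SAP Appendix 2).
3. Main estimand: the event is ignored (SAP 3.9, Table 3).
4. Primary analysis: the missing response is drawn in each of 20 datasets, each dataset is tested by CMH, and the results are combined by Rubin's rule (SAP 6.1, 6.3.1).
5. Hypothetical analysis: also imputed.
6. Composite analysis: non-response, through treatment discontinuation and through non-responder imputation of missing data.

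**Inputs.** SAP 1.3 gives 35 subjects per arm and assumed response rates of 70% (active) and 30% (placebo). The SAP does not give the probability of response in a draw. I assume 0.3 to 0.7, the span of the two planning rates.

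**The plan's own figure.** SAP 1.3 pairs 35 per arm with 85% power at two-sided 0.05. The usual formula with pooled variance under the null gives

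n = [1.960 × √(2 × 0.5 × 0.5) + 1.036 × √(0.7 × 0.3 + 0.3 × 0.7)]² / 0.4² = 26.5, so 27 per arm.

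Power at 35 per arm is 93.5% by the same method. The stated 35 is therefore not reproduced, but it errs on the safe side. Here it serves only as the arm size.

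**Effect of one death.** With draw probability q, the subject counts as a responder in 20q datasets on average, and the arm's averaged rate rises by q/35 compared with non-response.

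| q | Datasets as responder, of 20 | Added to arm rate |
|---|---|---|
| 0.3 | 6 | 0.3/35 = 0.9 points |
| 0.6 | 12 | 0.6/35 = 1.7 points |
| 0.7 | 14 | 0.7/35 = 2.0 points |

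The middle row is the pooled planning rate, (3 × 0.7 + 0.3)/4 = 0.6. It is roughly what a model without treatment would draw from if all three active arms met their assumed rate.

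**Cost of the alternative.** One death counted as non-response in an active arm lowers an expected 70% to 0.7 × 34/35 = 68.0%. Power against 30% at 35 per arm then goes from 93.5% to 90.6%.

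**Can it move a p-value across 0.05?** Only near the boundary. Take a chosen case, not a forecast, with a single stratum: 11 of 35 placebo responders, 19 of 35 active responders, and one active death among the other 16. The CMH test gives p = 0.055 with the death as non-response, and p = 0.032 (20 of 35) in any dataset where it is drawn as a response. The combined result mixes the two kinds of dataset.

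**The case against.** The strongest reply is that this is already covered and hardly matters. The composite analysis of the primary endpoint is pre-specified in SAP 6.3.2 and scores such a subject as a non-responder, so the conservative result will stand beside the main one. The largest effect, 2.0 points per death, is small against a planned difference of 40 points and a standard error of √(0.7 × 0.3/35) = 7.7 points for one arm. SAP 3.5 calls this a proof-of-concept study.

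The point about size stands, and it is why this is a minor point. The point about cover stands only in part. The composite analysis is supportive, and the primary test still carries the imputed response.

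A reader might infer four stronger things that the documents do not support:

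- **Every early death is imputed.** Under SAP 3.8.2 an early-termination visit can be assigned to the next scheduled visit. A subject who withdrew after Week 8, had that visit and then died may have an observed Week 12 value. The draws also come from a logistic model and are combined over 20 datasets, so this is not a single random assignment.
- **A death is likely.** The remark in Protocol 1.7 concerns another disease program and gives no count, denominator or follow-up time. Exclusion criterion 20 keeps out serious active infection, and Protocol 3.4.1 interrupts study drug for signs of infection. Neither document gives an expected death rate.
- **The plan is biased towards the active drugs.** Imputation raises the rate of whichever arm has the death, placebo included, and only against a non-response benchmark. If the model contained treatment arm, the draw would sit near that arm's own rate and leave it roughly unchanged.
- **Every analysis should be changed.** Counting deaths as non-response in the hypothetical analysis would override its rule that data after treatment discontinuation are treated as missing. For the EULAR disease activity and patient-reported indices (ESSDAI and ESSPRI), leaving post-death values unimputed would not help, because a mixed model for repeated measures still extrapolates as if the subject were alive. A worst rank in the rank analysis alone would make that sensitivity analysis target a different quantity from the model it checks.

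**Conclusion.** The point holds for the main analysis of the primary endpoint. As written, the general rule would give a subject who dies before Week 12 with no observed Week 12 value 20 imputed responses in the primary CMH analysis, under an estimand that has no meaning after death. The rule was not written with deaths in mind; it simply contains no exception for them.

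The size is 0.9 to 2.0 percentage points per such death in an arm of 35, relative to non-response. It rests on the assumed draw probability of 0.3 to 0.7 and on the planned arm size. It is zero if no such death occurs, and few are expected in 12 weeks. This is a minor defect in the primary estimand, worth correcting because the correction is nearly free.

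**What to change.** In SAP 3.9, in the treatment-policy column of Table 3 and in SAP 6.3.1, add a sentence to this effect: *In the main analysis of the primary endpoint, a death before the Week 12 assessment is counted as non-response and is not imputed.* The sentence should also say whether a value from an early-termination visit assigned to Week 12 counts as that assessment. Leave the hypothetical estimand as defined, and add no death rule to the repeated-measures or rank analyses under this point.

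The change should be made before any unblinded result can inform it. SAP Section 1 has the SAP finalized before the Week 24 analysis, and SAP 2.2 gives an internal team unblinded data during the study, so a rule added after a death could look driven by the data.

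The cost is one sentence in three places and a flag in the response dataset. There are two downsides. An arm with a death shows a slightly less favourable rate, and the main estimand becomes composite for death while remaining treatment policy for every other event, which its description should say.

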4. SUBJECT DISPOSITION

4.1. Subject Enrollment and Disposition

A summary of subject enrollment will be provided by treatment group for each country, investigator within a country and overall. The summary will present the number and percentage of subjects enrolled. For each column, the denominator for the percentage calculation will be the total number of subjects analyzed for that column.

A similar enrollment table will be provided by randomization stratum. The denominator for the percentage of subjects in the stratum will be the total number of enrolled subjects. If there are discrepancies in the value used for stratification assignment between the IWRS and the clinical database, the value collected in the clinical database or other source document will be used for the summary. A listing of subjects with discrepancies in the value used for stratification assignment between the IWRS and the clinical database or other source document at the time of data finalization will be provided.

The randomization schedule used for the study will be provided as an appendix to the CSR.

A summary of subject disposition will be provided for the entire study duration and by treatment phase. This summary will present the number of subjects screened, the number of subjects randomized, and the number of subjects in each of the categories listed below:

- Safety Analysis Set
- Completed Study
- Prematurely discontinued study with reasons for discontinuation
- Completed study drug
- Prematurely discontinued study drug with reasons for discontinuation

The study and drug disposition will also be presented by study period with the following categories:

- Completed study up to Week 12, Week 24, and through the end of the study
- Completed study drug up to Week 12, Week 24, and through the end of study
- Did not complete the study/study drug up to Week 12, Week 24, and through the end of study with reasons for premature discontinuation of the study
- Re-randomized at Week 24
- Continuing study drug (Week 24 Analysis only)
- Continuing study (Week 24 Analysis only)

For the status of study drug and study completion and reasons for premature discontinuation, the number and percentage of subjects in each category will be provided. The denominator for the percentage calculation will be the total number of subjects in the Safety Analysis Set corresponding to that column. In addition, a flowchart will be provided to depict the disposition.

Completion of the study up to Week 12 will be based on the presence of the corresponding visit in EDC or presence of Early Termination visit which is after Week 8 visit. Completion of treatment up to Week 12 is considered when the [date of last dose – date of first dose + 1] \geq 82 days (target date for Week 12 visit minus protocol allowed visit window). Similar algorithm is applied to Week 24 completion. Subjects are considered to complete 24 weeks of treatment if the start date of Week 24 treatment is provided or the [last dose date – first dose date + 1] \geq 166. Subjects who complete Week 24 visit/treatment but did not continue beyond Week 24 are reported as “Discontinued at Week 24”.

The by-subject listing of disposition will be provided by subject identification (ID) number in ascending order to support the above summary tables.

4.2. Extent of Study Drug Exposure and Adherence

Extent of exposure to study drug will be examined by assessing the total duration of exposure to study drug and the level of adherence to the study drug specified in the protocol.

4.2.1. Duration of Exposure to Study Drug

Total duration of exposure to study drug will be defined as the last dosing date of any study drug minus the first dosing date of any study drug plus 1, regardless of any temporary interruptions in study drug administration, and will be expressed in weeks using up to 1 decimal place (e.g. 4.5 weeks). For Week 24 primary analysis, the data cut-off date can be used as the last dosing date for subjects continuing on study.

For subjects with a partial last dosing date (i.e., month and year of last dose are known), the latest of the dispensing dates of study drug bottles, and the imputed last dose date [day imputed as last day of the month] will be used as the final imputed last dose date.

If only year is recorded (i.e., month and day of last dose are missing) or the entire date is missing then the latest of the dispensing month of study drug bottles, study drug start month, and study drug bottle return month will be used to impute the unknown last dose month (and a year if the entire date is missing). With the month imputed, the aforementioned method will be used to impute the last dose date. If the imputed date is after the date of death, choose the death date.

In addition, the duration of active treatment will be provided. The calculation for the subjects originally randomized to placebo will include the period starting from the first day of active study drug (Week 24 treatment start date is recorded on CRF).

The total duration of exposure to study drug will be summarized using descriptive statistics (number of subjects [n], mean, SD, median, Q1, Q3, minimum, and maximum) and the percentage of subjects exposed through the following time periods: Day 1, Weeks 2, 4, 8, 12, 16,

24, 30, 36, 42, and 48. The subject is considered to be exposed up to Week X if the last dose of any study drug is at least visit target day (per Table 2) minus protocol-allowed window (Appendix 1).

Summaries will be provided by treatment group for the Safety Analysis Set. No formal statistical testing is planned.

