7. SAFETY ANALYSES

The safety analyses will be performed for the placebo-controlled treatment period up to Week 24, and for the entire study duration. Analyses for these periods will be presented by the treatment groups specified in Section 3.

For the analyses of adverse events (AEs) that include data after Week 24 the exposure-adjusted analyses will be presented.

For the AEs, laboratory results and concomitant medication data, the collection/start date will be used to determine which reporting period the record belongs to. For other parameters collected on CRFs, the nominal visits will be used.

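### SAP 4.2.1 imputes partial or missing last-dose dates to month end and caps them only at death, so a last dose can be dated after all drug was returned or after study exit

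*SAP*

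**What the plan says.** SAP 4.2.1 has two branches for an incomplete last-dose date.

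- **Month and year known.** The last dose is "the latest of the dispensing dates of study drug bottles, and the imputed last dose date [day imputed as last day of the month"; that is, month end, or the latest dispensing date if that is later.
- **Month or whole date missing.** The latest of the dispensing month, "study drug start month, and study drug bottle return month will be used to impute the unknown last dose month". The first branch then supplies the day.

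One limit follows: "If the imputed date is after the date of death, choose the death date". The section also lets the data cut-off stand in as the last dosing date for subjects still on study at the Week 24 analysis, but it does not make the cut-off a limit on imputed dates. SAP 3.6.1 refers to Section 4.2.1 for this imputation and to no other rule.

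Exposure is "the last dosing date of any study drug minus the first dosing date of any study drug plus 1", ignoring interruptions. SAP 4.1 counts treatment as completed to Week 12 when that difference reaches "82 days (target date for Week 12 visit minus protocol allowed visit window", and uses 166 days for Week 24 unless a Week 24 treatment start date is recorded.

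**The concern.** A subject who has handed back every bottle, or who has left the study, cannot take a later dose. The rule can nevertheless produce one. In the first branch the bottle-return date is not consulted at all. In the second branch it is accepted as evidence of when dosing ended, but its day is dropped and the date moves past it to month end.

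The design makes a gap between last dose and bottle return possible. Protocol 3.1 and 3.4 let subjects who stop drug stay in the study and keep attending visits.

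The last-dose date feeds these outputs:
- duration of exposure and the percentage exposed through each week (SAP 4.2.1)
- treatment completion at Weeks 12 and 24 (SAP 4.1)
- treatment-emergent status of adverse events with incomplete onset dates (SAP 7.1.5.2)
- the 30-day laboratory window (SAP 7.2)
- the concomitant-medication summary (SAP 7.4.2)

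**Working it through.** **Inputs.** Target days of 85 (Week 12) and 169 (Week 24) come from SAP Table 2. The visit window of 3 days either side comes from SAP Appendix 1. The imputation rule is SAP 4.2.1.

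**1. The plan's thresholds.** Target day minus window gives 85 − 3 = 82 and 169 − 3 = 166. Both agree with SAP 4.1.

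**2. Size of the shift when the month is known.** A dose on the first of a 31-day month moves 30 days; a dose on the last day moves 0. In a month of L days the mean shift is (L − 1)/2. Assume true last doses are spread evenly over a 365-day year:

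(7 × 31 × 15 + 4 × 30 × 14.5 + 28 × 13.5)/365 = (3,255 + 1,740 + 378)/365 = 5,373/365 = 14.7 days.

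**3. Shortest true duration that can be counted as complete.** 82 − 30 = 52 days for Week 12; 166 − 30 = 136 days for Week 24.

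**4. Share misclassified.** A true duration of 82 − k days is counted as complete when the shift is at least k. For durations of 52 to 81 days, k runs from 1 to 30. The maximum shift is 30, so the probabilities of a shift of at least k, summed over k = 1 to 30, equal the mean shift. The share is 14.72/30 = 49%. The same holds for 136 to 165 days at Week 24, for subjects with no Week 24 treatment start date. Day-by-day enumeration over every start date in a year gives the same 49%.

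**5. Example, day missing (dates assumed).** First dose 8 January 2018, true last dose 2 March, all bottles returned at early termination on 5 March.
- True exposure: 24 + 28 + 2 = 54 days.
- SAP rule, 31 March: 24 + 28 + 31 = 83 days. This is at least 82, so the subject counts as a Week 12 treatment completer.
- Capped at 5 March: 57 days, not a completer.

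**6. Example, whole date missing.** Same subject, but bottles come back on 3 April. The SAP rule gives 30 April, or 24 + 28 + 31 + 30 = 113 days against a true 54, which is 59 too many. A cap at the return date gives 86 days. That removes the impossible part of the interval but still overstates, and the subject still passes 82.

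**7. The opposite direction.** Suppose the whole date is missing, the last bottles were dispensed at Week 12 (Day 85) on the last day of a month, and they were used to Week 18 (Day 127) but never returned. The rule then dates the last dose up to 127 − 85 = 42 days too early.

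**The case against.** The strongest reply is that this is a convention for a handful of records in descriptive tables. SAP 4.2.1 plans no formal testing of exposure. Protocol 9.1.5 requires start and end dates of study drug in source documents, and Protocol 9.1.6 provides for queries, so few dates should stay incomplete. Scheduled drug accountability also makes a long gap between stopping and return less likely. All of this stands and limits the size of the point. It does not make a dose after the last bottle came back correct.

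Four stronger readings are tempting, and the documents do not support them.

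- **That Week 12 completion in general is overstated.** Only completion of treatment uses the last-dose date. SAP 4.1 bases study completion on visits.
- **That adverse event rates are biased downward.** SAP 7 says: "For the analyses of adverse events (AEs) that include data after Week 24 the exposure-adjusted analyses will be presented". Exposure adjustment is thus not specified for the placebo-controlled comparison. A later last dose enlarges the denominator but also widens the 30-day event window, so the net direction is unknown. The denominator effect of one case is small: 30 days in an arm of 35 with full 336-day exposure (assumed) is 30/11,760 = 0.26%.
- **That efficacy results are affected.** The primary treatment-policy analysis disregards discontinuation (SAP Table 3). The hypothetical and composite estimands use treatment discontinuation as an event, but the SAP does not say which date marks it, so a link there cannot be shown.
- **That most affected early stoppers would be misclassified.** The share reaches 57% only for true durations of 57 to 81 days, the band nearest the threshold. Over 1 to 81 days it is 14.72/81 = 18%.

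A further objection concerns the remedy. SAP 4.2.2 anticipates bottles that are dispensed and never returned. A subject may return old bottles at Week 8, receive new ones that day and then be lost. A cap at the final bottle return or last visit would end that subject's dosing at about Day 57 with tablets still in hand, shortening both exposure and the safety window. This stands, and the cap must be conditional.

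**Conclusion.** The point holds as a minor defect. For subjects with a partial or missing last-dose date, SAP 4.2.1 can place the last dose after all drug was returned or after study exit, because death is the only limit.

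With the month known, the date is never too early relative to the true one and is 0 to 30 days late. The mean of about 15 days, and the 49% of affected subjects with true durations of 52 to 81 days counted as Week 12 treatment completers, both rest on last doses being spread evenly over the year. With the month or whole date missing, the error can be larger and can run either way, since unreturned bottles can lead to understatement.

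The documents give no count of incomplete dates, so the overall effect cannot be computed; it is probably small. It falls on exposure duration, percentage exposed, treatment completion and the 30-day post-dose windows.

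**What to change.** Add to SAP 4.2.1 that the imputed last-dose date may not exceed the earliest of:

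- date of death
- study completion or discontinuation date (the early termination visit where one took place)
- data cut-off, for the Week 24 analysis
- final bottle-return date, only when all dispensed bottles have been returned

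State also that the cap must not move the date before a recorded last-dose month, and that imputed last-dose dates are flagged in the listings.

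The cost is a few lines of SAP text, a small change to the date derivation and a check that every dispensed bottle is accounted for. Protocol 5.10 and 9.1.5 already require dispensing, return and study-completion dates to be recorded, and SAP 4.2.1 already uses dispensing and return information. No new data are needed. The cap removes impossible dates; it does not recover the true date, and it does not cure understatement when bottles are never returned.
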